**NCT NUMBER: NCT03328624**

**DATE OF DOCUMENT: OCTOBER 11, 2017**

## **A preliminary clinical usability study to assess design, comfort, wearability, and acceptance of Recovery Force's Deep vein thrombosis (DVT) cuff.**

### **Hypothesis**

The primary hypothesis for this Phase I study is following Recovery Force's DVT II cuff demonstration, participants will be strongly satisfied with design, comfort and wearability of the product. This will lead to a Phase II study, where it can be predicted that their perceived adherence to wearing the device will be high.

### **Outcome Measures**

Primary Outcome Measures are Wearability/Comfort and patient acceptance, which are the two key components for adherence and compliance to the product. This is evaluated through the Cuff Evaluation Questionnaire: For Assessment of cuff comfort, flexibility, temperature, ability of the cuff to remain in place on the leg, and sweatiness of the leg.

Secondary Outcome Measures are Usability and Design-Human Factors. This is designed to confirm that product and engineering requirements are in alignment. These outcome measures will provide feedback on compression, cycle sequence, target zones, materials, comfort, and mobility.

### **Methods and Study Design**

A single site, observational study will be conducted at the University of Southern California (USC) with participants who have and/or have had previous experience with DVT pneumatic cuffs. Study staff will examine participants overall experience, product functionality and perceived adherence to Recovery Force's DVT II cuff. About 46 participants will be recruited into the study. (Estimated recruitment duration – about 2 months)

### **Study Population and Inclusion Criteria**

Male or Female Age 18-65 who have had exposure with a DVT cuff on the calf within the last 6 months from a previous or current clinical condition will be enrolled to the study.

### **Recruitment**

Participants will be recruited from USC database, and referrals from physicians, clinicians, and vascular clinicians and staff. Study staff will obtain approval from the IRB and consent from each participant. All subjects will be consented individually in a private room. All study documents, including original signed consents, will be maintained for up to 10 years. Personal information regarding participation in this study may be disclosed if required by state law.

### **Tests and Procedures**

**Pre- Demonstrations Questionnaires:** Prior to beginning the prototype demonstration, participants and study staff will have completed an inclusion questionnaire with demographic

information and a Prior DVT Cuff Experience questionnaire. Demographics information includes Age, Gender, Ethnicity, Brief Medical History, Last Month of DVT Cuff use, Type of Prior DVT Cuff/Model.

**Prior Experience with DVT Devices Questionnaire:** A series of questions used to gauge patient experience with and attitudes towards DVT devices. Major topics will include the application and availability of DVT devices, perceptions regarding bothersome and pleasurable aspects of DVT devices.

**Prototype Demonstration:** Recovery Force will provide five DVT II prototypes for the study. Participants will test DVT II cuff prototype. Each participant will examine, wear, and remove a DVT Cuff for a total of 40 minutes test time and turn on the device for a minimum of 20 minutes. As participants try on the DVT II, they will be asked to mimic normal behavior (walking/sitting/standing/supine position).

**Post- Demonstrations Questionnaires:** The study will include primary and secondary outcome questionnaires that access human factor engineering and usability.

**Closing interview:** A closing interview of 20 min will be conducted by the study team. A series of follow-up post-demonstration questions using a semi-structured interview with an interpretative phenomenological analysis approach will be recorded and transcribed by a study staff. This interview will focus on initial exposure to the device, user impressions, suggestions, critiques and overall appeal.

### **Sample size calculation**

Using a sample power analysis (IBM SPSS), the PI determined 34 total patients will be needed, using an error margin of 0.2 points based on overall expected responses to questionnaires, assuming 10% missing data, alpha level of 95% certainty. Assuming a 25% dropout rate, the recruitment goal will increase to 46 participants.

The small sample size was also recommended as a preliminary assessment of product design and human factor usability that will provide adequate insight into clinical protocol design for future larger statistically powered clinical trials in Phase II to address patient compliance.

Overall patient acceptance will be determined by the patient's response to the final question on the End of Study Cuff Evaluation Questionnaire: "Which Cuff did you like better OVERALL?" If at least 75% of patients respond as preferring the new cuff over the traditional, then the study's primary outcome will be achieved.

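### The 75% rule measures preference over each participant's own earlier cuff, so it does not test the hypothesis of strong satisfaction and cannot alone establish acceptance

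*Combined protocol and SAP*

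**What the plan says.** The Hypothesis section is worded in absolute terms: "participants will be strongly satisfied with design, comfort and wearability of the product". The Outcome Measures section then states "Primary Outcome Measures are Wearability/Comfort and patient acceptance", and presents these two as the key components of adherence. It describes the Cuff Evaluation Questionnaire as covering "Assessment of cuff comfort, flexibility, temperature, ability of the cuff to remain in place on the leg, and sweatiness of the leg".

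The only success rule is in the Sample size calculation section. There, "Overall patient acceptance will be determined by the patient's response to the final question" of the questionnaire, worded "Which Cuff did you like better OVERALL". The primary outcome is achieved "If at least 75% of patients respond as preferring the new cuff over the traditional". No scoring rule or threshold is given for the comfort and wearability items, and they play no part in the decision.

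The comparator is not standardised. The inclusion criteria admit people with calf-cuff exposure in the last 6 months. Tests and Procedures records the type or model of the prior cuff, and a questionnaire collects "perceptions regarding bothersome and pleasurable aspects of DVT devices". The only device that section describes participants testing is the DVT II prototype.

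**The concern.** A question about which of two cuffs was liked better has no zero point. A participant who found the new cuff uncomfortable, but less so than the old one, is counted as accepting it. A participant content with both who slightly favours the old one is counted against it. The percentage therefore reflects opinion of the old cuffs as well as of the new one, and the old cuffs vary from person to person.

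The stated hypothesis concerns satisfaction with the new product, and the plan expects it to lead to a Phase II study with high perceived adherence. If a preference result is reported as acceptance, that later study could be designed on a claim the data do not support. Equally, a satisfactory cuff could be recorded as a failure.

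**Working it through.** **1. The plan's own figure.** The recruitment goal reproduces: 34 / (1 − 0.25) = 45.3, rounded up to 46. The 34 rests on a margin of 0.2 questionnaire points, not on the 75% proportion. No standard deviation is given, so the 34 itself cannot be checked. None of this bears on what the deciding item measures.

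**2. Hypothesis and rule side by side.**

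| | Hypothesis | Success rule |
|---|---|---|
| Quantity | Satisfaction with the new cuff | Liking of new cuff minus liking of old cuff |
| Reference point | A level of satisfaction | The participant's own prior cuff |
| Dislikes both, new one less | Not satisfied | Counts as acceptance |
| Likes both, old one slightly more | May be satisfied | Counts against acceptance |

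The last two rows show that neither statement implies the other. This follows from the wording alone.

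**3. Chance of meeting the rule.** With 34 evaluable participants, at least 75% means 0.75 × 34 = 25.5, so 26 or more. From the binomial upper tail, P(X ≥ 26) is 0.1% at a true preference of 50%, 27% at 70%, 51% at 75%, 77% at 80% and 94% at 85%.

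**4. Illustration A: same new cuff, different prior attitudes.** These rates are assumed and are not in the documents: 95% of people dissatisfied with their old cuff choose the new one, and 55% of the rest do.

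| Share dissatisfied | Preference rate | 26 of 34 | 24 of 31 | 35 of 46 |
|---|---|---|---|---|
| 30% | 0.3×0.95 + 0.7×0.55 = 67% | 16% | 15% | 12% |
| 50% | 0.5×0.95 + 0.5×0.55 = 75% | 51% | 47% | 51% |
| 70% | 0.7×0.95 + 0.3×0.55 = 83% | 89% | 86% | 92% |

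The 31 is 34 less 10% missing (30.6, rounded up), and 46 is the recruitment goal. The choice of n does not change the pattern.

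**5. Illustration B: new cuff held fixed, old cuff varied.** Also assumed: normally distributed liking scores on a 5-point scale, SD 1 for each cuff, correlation ρ from 0 to 0.5, and satisfied meaning a score of 3.5 or more. With a new-cuff mean of 3.0, the share satisfied is 1 − Φ(0.5) = 31%. The preference rate is Φ((mean new − mean old) / √(2(1 − ρ))).

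| Old-cuff mean | Prefer new cuff | Chance of 26 of 34 |
|---|---|---|
| 1.5 | 86–93% | 95% to nearly 100% |
| 2.0 | 76–84% | 57–92% |
| 2.5 | 64–69% | 8–23% |
| 3.0 | 50% | 0.1% |

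In the other direction, a new cuff with mean 4.0 (69% satisfied) against an old cuff also at 4.0 gives 50% preference and a 0.1% chance of success.

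**The case against.** For a possible replacement device, preference over the existing one is a legitimate endpoint. The plan openly defines acceptance that way, and it recruits people who have worn such a cuff. A reader might infer that acceptance must by its nature be absolute. The documents do not say so: Outcome Measures describes "patient acceptance, which are the two key components for adherence and compliance to the product" without requiring an absolute rating. What remains is the mismatch with the plan's own hypothesis, which is absolute.

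Nor is it right to infer that the plan ignores how participants find the new cuff. Wearability/comfort is a separate primary outcome, and the closing interview covers impressions and critiques. A poorly rated cuff could show up there. Neither source, however, enters the 75% rule, and wearability/comfort has no scoring rule.

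A reader might also assume that absolute ratings of the new cuff are certain to be available. The documents list topics only. They show no response scale, and they do not say whether the items rate the new cuff alone or compare the two. The 0.2-point margin suggests a point scale but does not settle this. That objection stands and limits the remedy.

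Finally, the study is preliminary, and part of the pass/fail swing comes from applying a bare cutoff in a small sample: at n = 34 and 75%, the 95% half-width is 1.96 × √(0.75 × 0.25 / 34), about 14.6 percentage points. That is a separate matter. Small size does not remove the mismatch, because the plan intends these results to inform the design of later trials on compliance.

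**Conclusion.** The point holds as a mismatch between the hypothesis and the rule used to declare success. The rule can be met when participants are not satisfied with the new cuff, and missed when they are. The direction rests only on the text.

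The size is illustrative. Under the assumed preference rates of 67%, 75% and 83%, the chance of meeting the rule at n = 34 is 16%, 51% and 89%. A reader might take these figures as the expected instability of this study, or conclude that the rule is tilted towards success. The documents support neither: they give no data on attitudes to prior cuffs, and the mismatch can work in either direction.

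The plan can run as written. What changes is what it may conclude.

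**What to change.** - In the Sample size calculation section, call the 75% result preference over the prior cuff, and do not use it alone to conclude acceptance or satisfaction.
- Base the statement on satisfaction and acceptance on the new-cuff comfort and wearability responses in the Cuff Evaluation Questionnaire. Fix the favourable categories in advance on the actual form, and report the preference percentage beside them.
- Tabulate preference by those ratings, and by prior cuff model and Prior Experience responses.
- If the form's items turn out to be only comparative, limit the conclusion to preference.

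A composite that requires both choosing the new cuff and rating it above a midpoint, with the 75% cutoff kept, should not be adopted. No midpoint is documented, and the composite still moves with prior attitudes: if 75% of those choosing the new cuff rate it well, the three samples in Illustration A give 0.75 × 67%, 75% and 83%, or about 50%, 56% and 62%. It can also be nearly unattainable. If 24 of 31 prefer the new cuff and 6 of those 24 rate it poorly, 18 of 31 (58%) qualify, and a true rate of 58% has about a 2% chance of reaching 24 of 31.

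The cost is revised wording, a narrower headline claim, and descriptive tables with small cells. If the form holds ratings of the new cuff, no new data are needed.

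### The only success rule judges patient acceptance, one of two primary outcomes, but is said to settle the study's primary outcome as a whole

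*Combined protocol and SAP*

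**What the plan says.** All references are to the combined protocol and SAP.

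- **Outcome Measures** names two primary outcomes: "Primary Outcome Measures are Wearability/Comfort and patient acceptance, which are the two key components for adherence and compliance to the product". Both are evaluated through the Cuff Evaluation Questionnaire, described as "For Assessment of cuff comfort, flexibility, temperature, ability of the cuff to remain in place on the leg, and sweatiness of the leg". No score, response scale or cut-off is given.
- **Hypothesis** states the primary hypothesis in absolute terms: "participants will be strongly satisfied with design, comfort and wearability of the product". It continues: "This will lead to a Phase II study, where it can be predicted that their perceived adherence to wearing the device will be high".
- **Sample size calculation** assigns a closing preference item to one of the two primary outcomes: "Overall patient acceptance will be determined by the patient's response to the final question on the End of Study Cuff Evaluation Questionnaire". The next sentence gives the only success rule in the document: "If at least 75% of patients respond as preferring the new cuff over the traditional, then the study's primary outcome will be achieved".
- The same section sizes the study at 34 patients from a margin of 0.2 points on questionnaire responses, with 10% missing data and 95% confidence. It raises the recruitment goal to 46 for 25% dropout.

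**The concern.** The rule is attached to patient acceptance, but its stated consequence covers the whole primary outcome. Wearability/comfort, the other primary outcome, does not enter the rule and has no visible criterion of its own.

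The rule also measures something different from the hypothesis. Liking the new cuff better than a traditional one is a comparison, whereas strong satisfaction is a level. A participant who found both cuffs uncomfortable may still favour the new one.

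Followed as written, the study could report primary success whatever the comfort responses show. The Hypothesis section then looks ahead to high perceived adherence in Phase II. Outcome Measures says adherence rests on both components, and only one of them would have been judged.

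**Working it through.** **1. The plan's own figures.**

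Recruitment goal: 34 / (1 − 0.25) = 45.3, rounded up to 46. This matches the plan.

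The base of 34 cannot be confirmed, because no standard deviation (SD) is stated. For estimating a mean score, n = (1.96 × SD / 0.2)², divided by 0.9 for missing data. With an assumed SD of 0.55, n = 5.39² = 29.05, rounded up to 30, and 30 / 0.9 = 33.3, rounded up to 34. Other assumed SDs give 18 (SD 0.4), 28 (0.5), 39 (0.6) and 108 (1.0).

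If the 0.2 were instead a margin on a proportion p, then n = 1.96² × p(1 − p) / 0.2². That gives 25, then 28 after missing data, at p = 0.5, and 19, then 22, at p = 0.75. Neither is 34. The sample size therefore reads as a precision target for questionnaire scores. It is neither a success criterion nor derived from the 75% rule.

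**2. What is claimed against what is judged.**

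| Item | Section | Visible success criterion |
|---|---|---|
| Primary outcome: patient acceptance | Outcome Measures | At least 75% favour the new cuff (Sample size calculation) |
| Primary outcome: wearability/comfort | Outcome Measures | None |
| Hypothesis: strong satisfaction | Hypothesis | None |

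One of two primary outcomes has a criterion.

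**3. What the rule needs.**

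If all 34 answer the item, 0.75 × 34 = 25.5, so 26 must favour the new cuff. 26/34 = 76.5% (Wilson 95% interval about 60% to 88%), and 25/34 = 73.5% falls short. The exact binomial chance of meeting the rule is 0.27, 0.51, 0.77 and 0.94 if the true preference is 70%, 75%, 80% and 85%. These figures depend only on the preference proportion; no comfort score enters them. The documents give no input from which a matching figure for wearability/comfort could be computed.

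**4. Two constructed cases.**

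- 26 of 34 favour the new cuff and every comfort rating is poor: the rule is met.
- 25 of 34 favour the new cuff and every comfort rating is excellent: the rule is missed.

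The verdict on the study's primary outcome can therefore differ from the comfort results in either direction.

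**The case against.** The best defence is that comfort and acceptance were meant as one construct on one instrument, with the overall preference item as its summary. Outcome Measures itself turns to the singular when it says how the two are evaluated, so this reading is possible. But the plan does not state it. Sample size calculation labels the item patient acceptance, which Outcome Measures lists separately from wearability/comfort. Even as a summary, a comparison with a traditional cuff cannot establish a level of satisfaction.

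A second defence is that the 0.2-point margin shows the questionnaire scores were to be estimated with stated precision and not passed or failed. That is reasonable for a preliminary study, and it stands: a cut-off for every primary measure is not required. It does not rescue a rule that credits one item with the whole primary outcome.

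Three stronger readings are tempting but go beyond the documents:

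- *The hypothesis cannot be tested.* The questionnaires are not shown, and strong satisfaction may be a response category on one of them. What can be said is that no criterion is visible.
- *Preference says nothing about comfort or satisfaction.* It is indirect evidence on both, though not a test of either.
- *Phase II depends on the 75% rule.* No section makes it formally conditional. Sample size calculation leaves compliance to later, larger trials.

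The hypothesis also mentions design, which Outcome Measures places elsewhere: "Secondary Outcome Measures are Usability and Design-Human Factors". That is a side mismatch and the point does not rest on it.

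**Conclusion.** The concern holds in this form: a rule that judges one of two primary outcomes is said to achieve the study's primary outcome, and it does not test the stated hypothesis of strong satisfaction. The contradiction lies between sections of the visible text and does not depend on any sample-size calculation. The absence of a wearability/comfort criterion is claimed for the visible text only, since the questionnaire and reference 29 are not shown.

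The point is worth fixing, at the low end of that grade. The study is a preliminary usability assessment, the comfort data are collected in any case, and the correction is small.

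A reader might infer that preference should simply become the sole primary outcome. The documents do not support that as a change of wording alone. The 34 patients were sized on questionnaire scores, so a sole preference outcome would have no stated sample-size basis. The comparison may also rest on recall: Study Population and Inclusion Criteria asks for cuff exposure within the last 6 months, and Tests and Procedures describes wearing only the DVT II.

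**What to change.** 1. In Sample size calculation, end the success rule with: *the patient-acceptance primary outcome will be considered met; this does not by itself establish strong satisfaction or wearability/comfort*.
2. Keep wearability/comfort as a primary outcome and report it separately, as questionnaire scores with 95% confidence intervals. This fits the 0.2-point margin used to size the study.
3. If the strong-satisfaction hypothesis is to be judged, name the score and fix the cut-off on the questionnaire's actual response scale before data are seen. State whether both primary outcomes must be met. Otherwise, reword the hypothesis, including its reference to design, to match what is tested.

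**Cost.** Steps 1 and 2 need a few sentences and no new data. Step 3 needs either a rewording or a score and cut-off agreed in advance; an added item would be needed only if design is to be judged and the questionnaires do not cover it. The downside is a narrower success claim, or one that is harder to meet if both outcomes are required.

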### **Potential Risks**

Risks will be explained to all participants in advance of study enrollment. The main risk is slight discomfort from improper use of shoe by over/under tightening the closures. A user manual will be provided to each participant. A second risk is the amount of pressure applied to the bottom of the foot may cause slight discomfort. Participants may opt not to participate in the study at any time; additional participants will be recruited through the pool of eligible participants.

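### The only two risks named in the protocol concern a shoe and the sole of the foot, but the device under study is described as a cuff

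*Combined protocol and SAP*

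**What the plan says.** The Potential Risks section opens with a commitment: "Risks will be explained to all participants in advance of study enrollment". It then names two risks. The first is "The main risk is slight discomfort from improper use of shoe by over/under tightening the closures". The second is "A second risk is the amount of pressure applied to the bottom of the foot may cause slight discomfort". Between the two it adds "A user manual will be provided to each participant", without saying which device the manual covers.

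The other sections describe a different kind of product. The title calls it a DVT cuff, and the Hypothesis refers to the "DVT II cuff demonstration, participants will be strongly satisfied with design, comfort and wearability of the product". Under Outcome Measures, the primary questionnaire covers, among other things, "ability of the cuff to remain in place on the leg, and sweatiness of the leg". Methods and Study Design, Tests and Procedures, and the acceptance criterion under Sample size calculation also call the product a cuff. The closing section, Importance of the Knowledge to be Gained, judges the study's risk-to-knowledge balance reasonable on the ground that the risks are minimal.

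**The concern.** A protocol's risk section should describe the hazards of the device that participants will wear. Here, one named risk is tied to a shoe and the other to the sole of the foot, and neither item appears anywhere else in the document.

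Two things depend on that section. The first is the explanation given before enrollment. If staff follow the text as written, they will describe the risks of a shoe and of sole pressure to people who will put on and switch on a cuff. The second is ethics review. A board reading this document cannot match the minimal-risk statement to risks worded for the described device.

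**Working it through.** No formula applies, and the plan gives no figure to reproduce. The check sets the sections side by side and counts words from the title to the last section.

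**What the study product is called**

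The word cuff (or cuffs) occurs 16 times. Sorted by what it refers to:

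- Study product, 8: title and Hypothesis 2, Outcome Measures 2, Methods and Study Design 1, Tests and Procedures 2, Sample size calculation 1.
- Cuffs the participants used previously, 5: Methods and Study Design 1, Study Population and Inclusion Criteria 1, Tests and Procedures 3.
- Questionnaire name or generic use, 3: Outcome Measures 1, Sample size calculation 2.
- Check: 8 + 5 + 3 = 16.

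The name DVT II occurs 5 times, and 3 of these are followed directly by the word cuff. In the Potential Risks section, cuff occurs 0 times.

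**What the risk section refers to**

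- Shoe: 1 occurrence in the whole document, in Potential Risks.
- Foot: 1 occurrence, in Potential Risks.
- Closures: 1 occurrence, in Potential Risks.
- Leg: 2 occurrences, both in the questionnaire sentence under Outcome Measures.

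**Taking the two risks in turn**

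1. *Tightening of closures.* If the word cuff is put in place of shoe, the sentence could describe a cuff that fastens around the leg. The documents neither confirm nor rule this out, because no other section mentions how the DVT II is fastened.
2. *Pressure on the sole.* Changing one noun does not repair this sentence, because the body site itself appears nowhere else. The calf is mentioned under Study Population and Inclusion Criteria, but that concerns the prior device and is not evidence about the DVT II.

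**Could the device have a foot part?**

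Three features of the text leave this open. Outcome Measures says "These outcome measures will provide feedback on compression, cycle sequence, target zones, materials, comfort, and mobility" but never defines the zones. Potential Benefits speaks broadly of the lower limb. Tests and Procedures gives no physical description of the DVT II. What the text supports is therefore a mismatch between the risk section and the described product. It does not prove that a foot component is absent.

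**Planned exposure**

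Methods and Study Design gives the planned number: "DVT II cuff. About 46 participants will be recruited into the study". Tests and Procedures gives each participant 40 minutes of testing, with the device running for at least 20 of them. These figures describe the planned audience for the risk explanation. They are not evidence that anyone was misinformed.

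**The case against.** The strongest reply accepts the mismatch and disputes its consequences.

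- *The effect on consent is not shown.* The protocol does not say that this paragraph is the script for the consent discussion, and the consent form is not available for this review. This stands: what participants were told cannot be judged. The section still commits to explaining risks, and the only risks it supplies are these two.
- *The minimal-risk statement has other support.* It does not cite the risk section. Exposure is short, participants are aged 18 to 65 and must have had a DVT cuff on the calf within the last 6 months, and both named risks are only slight discomfort. This stands as context, and nothing in the documents shows that corrected wording would overturn the conclusion. Exposure time and prior cuff use bear on how large a risk may be. They do not identify the risks of this device.
- *Half of the problem may be one wrong noun.* This is fair for the tightening risk, so the two risks should not carry equal weight. It does not explain the sole-pressure sentence.
- *A foot component may exist.* This cannot be excluded. If it does exist, the device description is incomplete, and the sections still have to be reconciled.

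**Conclusion.** The concern holds. Both of the protocol's named risks (2 of 2) are worded for a shoe or the sole of the foot, while the study product is called a cuff 8 times across five sections (counting the title with the Hypothesis) and never in the risk section. Confidence in the textual mismatch is high. Its effect on what participants learned is unknown.

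The matter is more than a stray typing error, because it covers the whole risk list and that list bears on the explanation promised before enrollment. It is also limited: the design, sample size, outcomes and acceptance criterion are untouched. It should be corrected, but it does not threaten the study's results. The conclusion assumes that the available text is the full device description. A description or figure elsewhere that shows a foot component would change which section needs editing, but not the need to reconcile them.

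**What to change.** Reconcile Potential Risks with the title and Hypothesis, Outcome Measures, and Tests and Procedures, in one of two ways:

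- if the device has no foot component, replace the shoe and foot wording with the risks the sponsor has identified for the DVT II cuff; or
- if it has one, describe that component under Tests and Procedures and make the risk wording agree with that description.

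Then check three further items for the same mismatch: the user manual, including which device it covers; the consent form; and the minimal-risk statement under Importance of the Knowledge to be Gained.

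The cost is a change of protocol wording, consent wording if it is affected, and an IRB amendment. Design, sample size and analysis stay as they are.

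### A participant who withdraws during wear because of discomfort has no planned route into the comfort data, and nothing records early cuff removal, its time or its reason

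*Combined protocol and SAP*

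**What the plan says.** The Potential Risks section of the combined protocol and SAP names two risks, and both are discomfort: "The main risk is slight discomfort from improper use of shoe by over/under tightening the closures" and "A second risk is the amount of pressure applied to the bottom of the foot may cause slight discomfort". The same section deals with leaving the study in one sentence: "Participants may opt not to participate in the study at any time; additional participants will be recruited through the pool of eligible participants".

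Outcome Measures makes comfort primary: "Primary Outcome Measures are Wearability/Comfort and patient acceptance, which are the two key components for adherence and compliance to the product". The instrument is the Cuff Evaluation Questionnaire, described there as "For Assessment of cuff comfort, flexibility, temperature, ability of the cuff to remain in place on the leg, and sweatiness of the leg".

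Tests and Procedures sets the order of the session. The questionnaires completed beforehand cover demographics and earlier DVT devices. The participant then has a 40-minute test of the prototype, with the device switched on for at least 20 of those minutes. Under the heading for questionnaires after the demonstration it says: "The study will include primary and secondary outcome questionnaires that access human factor engineering and usability". The closing interview is "A series of follow-up post-demonstration questions using a semi-structured interview with an interpretative phenomenological analysis approach". The Sample size calculation section calls the instrument the End of Study Cuff Evaluation Questionnaire.

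The text describes no record of minutes worn, of early removal or of the reason for it. It also describes no adverse event collection and no assessment of someone who leaves part-way.

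**The concern.** In a wearability study, a participant who stops because the cuff is uncomfortable gives one of the most informative results available. It is an occurrence of the kind of harm the plan foresees and a poor score on a primary outcome at once. Here it may leave no trace. The ratings come at the end, the person may already have gone, and another participant is recruited.

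Two things are at stake. First, comfort, temperature and sweatiness may be rated mainly by those who tolerated the cuff, so missing ratings would be linked to the outcome itself. Second, the study could not say how many wearers stopped for discomfort. The Hypothesis section uses satisfaction with comfort to predict high perceived adherence in Phase II, and early removal bears directly on that prediction. Data of this kind that are not collected on the day cannot be recovered at analysis.

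**Working it through.** **1. The plan's own figure.** Inputs from the Sample size calculation section: 34 patients needed, 25% dropout, goal 46.

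34 / (1 − 0.25) = 45.33, rounded up to 46. This reproduces the plan.

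46 − 34 = 12, and 12 / 46 = 26%. The plan therefore allows for 12 recruited people who drop out. It gives no reason or timing for these losses, and some may occur before a cuff is worn. The 34 already carries a further 10% allowance for missing data (34 × 0.9 = 30.6), also without stated reasons.

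**2. Three participants followed through the written procedure.**

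- *Wears the cuff for the full test.* Reaches the questionnaires and interview. Comfort is captured.
- *Takes the cuff off early and stays.* Nothing makes the questionnaires or interview conditional on completing 40 minutes, so comfort can still be captured. The early removal, its time and its reason have no planned record.
- *Withdraws during wear because of discomfort.* The questionnaires given beforehand concern other devices, and the instruments that rate the new cuff come later. No step captures this person's view of the cuff or the reason for leaving. The only stated consequence is that additional participants are recruited.

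The gap in the comfort ratings concerns the third participant. The gap in recording early removal concerns the second and third.

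**3. Direction of the bias.** Let n wearers give a rating with mean M_r, with higher scores meaning more comfort. Let k wearers withdraw unrated, and let M_w be the mean they would have given.

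Mean over all wearers = (n × M_r + k × M_w) / (n + k)

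Reported mean − mean over all wearers = [k / (n + k)] × (M_r − M_w)

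If the k people left because of discomfort, M_w should lie below M_r, so the reported mean is too favourable. Replacement adds to n but does nothing to recover M_w.

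**4. Size of the bias.** Neither term can be filled in from the documents. If nobody withdraws during wear, k = 0 and the bias is zero. With n = 34 and k = 12, the weight k / (n + k) is 12 / 46 = 0.26. That assumes that every allowed loss put the cuff on and withdrew during wear, which the plan does not say. The weight then multiplies a difference M_r − M_w for which the plan gives no basis. Nor is 12 a firm ceiling, since the plan sets no limit on additional recruitment. The direction follows from the reasoning in step 3, but no size does.

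**The case against.** The strongest reply is that the loss is inferred from silence. Taking the cuff off is itself part of the procedure, the questionnaires are the next step listed, and the interview invites critiques. Staff could give both to anyone who stops early. Exposure is one short session, the foreseen discomfort is described as slight, and this is a preliminary usability study that leaves compliance to Phase II. All of that stands and limits the point. It does not close the gap for someone who withdraws during wear, because nothing requires staff to ask.

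Three stronger readings are tempting, and the documents do not support them.

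- *Early removal takes a person out of the data.* Removing the cuff is not the same as withdrawing from the study. The Potential Risks section says only that additional participants are recruited, not that leavers' data are discarded.
- *The bias can be sized by counting the 12 allowed losses as discomfort failures.* This assumes that all 12 wore the cuff, ignores replacement, and needs a proportion finding the cuff comfortable. The plan defines no such endpoint; its sample size rests on a margin of 0.2 points.
- *The study must count stoppages to support its statement that risks are minimal.* That statement, in the section on the importance of the knowledge to be gained, is an advance justification of the study and not a result it has to show.

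**Conclusion.** The point holds in a limited form. Discomfort is both the only named harm and part of a primary outcome, and the plan does not say how a wearer who stops early is assessed or counted. Someone who withdraws during wear because of discomfort has no planned way to contribute to the comfort result and may be replaced. If that happens, the result is biased towards comfortable by an amount that the documents do not allow to be estimated; it is zero if nobody withdraws in this way.

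This rests on two assumptions: that such withdrawals can occur, and that those people would have rated comfort lower than those who stayed. The questionnaires and any session form are not reproduced in the document. If a form already records wear time and reason for removal, only the counting rule remains to be written.

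No figure in the plan is wrong because of this. It is a low-cost improvement to data capture, separate from the question of which denominator the 75% preference rule should use.

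**What to change.** In Tests and Procedures and Potential Risks, state that:

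- the Cuff Evaluation Questionnaire is offered when the cuff comes off, whether as planned or early, and the participant remains free to decline;
- minutes worn and the reason for removal are recorded for everyone who puts the cuff on;
- early removal for discomfort is reported as a count over all wearers;
- early removers' ratings are included in the comfort summary where given;
- replacements are recruited in addition to those wearers, not instead of them.

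The cost is two fields on the session form and short additions to two sections, with no extra visit. The comfort result may look less favourable.

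Separately, the risk text refers to a shoe and to pressure under the foot, while Study Population and Inclusion Criteria concerns a cuff on the calf. These sections must be reconciled so that the discomfort recorded matches the device tested.
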